The incidence of elevated ICP is more than 50% in patients with ICP ranging as high as 80% in patients with traumatic brain injury.^{10, 11} The fundamental goal of management in TBI is based on managing ICP, maintaining adequate CPP and is based upon the Monro-Kellie doctrine and cerebral autoregulation.¹¹ Similarly incidence of raised intracranial pressure in patient with intracranial hemorrhage ranges from 36% to 80%.¹² Malignant cerebral edema leading to raised intra-cranial pressure is a major cause of adverse outcome in patients with acute ischemic stroke with an incidence of 10-20%. Use of osmotic therapy in such patients has been recommended in both ENLS guidelines for management of intra-cerebral hemorrhage and AHA/ASA guidelines.¹³

Mannitol, is a polyol (sugar and alcohol) a hyper-osmolar agent that has been used for osmotherapy in neurosurgical patients since many years. The proposed mechanism of its action are transient hypervolemia thus decreasing blood viscosity, increase in CBF and the microvascular circulation leading to autoregulatory vasoconstriction and thus reducing cerebral blood volume.¹⁴ However there is controversy regarding its mechanism of effect when given as single bolus dose. Its effect in red blood cell rheology and improved oxygen delivery/circulation has also been hypothesized for explaining its immediate effect in decreasing ICP¹⁴. Another hypothesis argues about the ability of Mannitol to lower intracranial pressure by reducing brain water content (diuretic effect)⁹ and decreasing CSF production.

Pharmacokinetics of Mannitol:

Onset of action: 15 minutes

Half life: 100 minutes

Osmolarity: 1100 for 20% Mannitol

Duration of action: 3-6 hours

Excretion: Urine (80%)

Time of peak action: 30- 100 minutes

Literature review:

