Optic nerve sheath diameter measurement is a common acute care sonographic procedure. Since the change in intracranial pressure is a continuum of event, sonographic monitoring of such an event is possible through optic nerve sheath diameter monitoring. Mannitol is a common drug used in patients/subjects with raised intracranial pressure either due to trauma, subarachnoid haemorrhage or stroke. Its effects on intracranial pressure reduction are well known though the mechanism is not properly understood yet. My study/research aims at studying the pattern and extent of change in the optic nerve sheath diameter after osmotherapy with intravenous 20% Mannitol within its time of peak effect. Monitoring such changes can help tailor the treatment modality and tier according to efficacy. In absence of invasive monitoring in a limited setup like ours and in light of the various complications associated with invasive monitoring, noninvasive monitoring can help us in improving the outcomes in such neurosurgical or neurological cases.

5. Objectives

General:

To study the effect of intravenous administration of 20% Mannitol on the optic nerve sheath diameter in patients with raised intracranial pressure.

Specific:

- To compare the changes in optic nerve sheath diameter brought about by administration of Mannitol within the time of its peak effect.
- To correlate and compare the extent of change in ONSD (Δ ONSD) at 30, 60 and 120 minutes in relation with dose of mannitol administered and change in Mean Arterial Pressure (Δ MAP).
- To correlate the changes in ONSD in relation with PIP and PEEP in patients on Mechanical ventilation.

6. Research Questions/Hypothesis:

Null Hypothesis (H_0): Serial Optic nerve sheath diameter monitoring with a cut-off value of 5.0 mm can reflect changes due to IV administration of 20% Mannitol in patients with raised ICP.

Alternate Hypothesis (H_1): Serial Optic nerve sheath diameter monitoring with a cut-off value of 5.0 mm cannot reflect changes due to IV administration of 20% Mannitol in patients with raised ICP.

Expected outcome: $H_0 \neq H_1$

7. Research Design and Methodology

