7.6 Sample size

Basis and method of determination including power of the study, level of significance etc.

Power of study: 80% ($1-\beta = 0.84$)

Level of significance: 95% ($\alpha = 0.05$)

Assuming mean difference and standard deviation of differences (σ) of 0.24 and 0.49 respectively, effect size (Δ) was 0.49 as derived from previous study²³,

Using the formula

$$N = \frac{(z_{1-\alpha/2} + z_{1-\beta})^2}{\Delta^2} + \frac{z_{1-\alpha/2}^2}{2},$$

The sample size required would be 35.

Assuming a dropout of 10%, the required sample size would be 40.

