7.7 Inclusion and Exclusion Criteria

Inclusion criteria:

- Age > 18 yrs
- Gender: any
- H/o traumatic brain injury/ subarachnoid hemorrhage/ acute stroke
- Mean optic nerve sheath diameter > 5mm (0.5cm)
- Under osmotherapy with 20% Mannitol.

Exclusion criteria:

- Baseline ocular pathology like tumors, Grave's disease and Sarcoidosis
- Previous ocular surgery
- Decompressive cranial surgery

7.8 Study Variables:

Epidemiological variables:

- Age
- Gender
- Weight
- BMI

Measured base line variables:

- GCS score
- Mean arterial pressure
- Optic nerve sheath diameter, T₁ (mean of 3 measurements in each eye)
- Ventilator parameters (PIP and PEEP) in patients on mechanical ventilation.

Measured variables after infusion of 20% Mannitol:

- Dose of 20% mannitol administered
- Mean arterial pressure
- Optic nerve sheath diameter (mean of 3 measurements in each eye) after 30mins(T₂), 60 mins(T₃) and 120 mins(T₄).

7.9 Primary outcomes:

Change in the optic nerve sheath diameter (Δ ONSD) at T₂, T₃ and T₄.

7.10 Secondary outcomes:

- Change in the mean arterial pressure before and after mannitol administration.
- Comparison and correlation between the extent of change in ONSD (Δ ONSD) with dose of mannitol and change in MAP(Δ MAP).
- Correlation between Δ ONSD with PIP and PEEP in mechanically ventilated patients

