7.13 Plan for Data Management and Statistical Analysis

- Data will be entered by the investigator and resident on duty in the intensive care unit and will be destroyed after the completion of the study, however the results and conclusions will be stored without hampering the subject/ patient's privacy or rights.
- Power of the study is based on the primary outcome which is the change in ONSD following infusion of 20% Mannitol.
- Paired t test, chi square test will be used for data analysis.
- Data will be analysed by using SPSS 20 software version
- The value of $p < 0.05$ will be considered as statistically significant.

7.14 A graphic outline of the study design and procedures using a flow diagram including the timing of assessments.

8. Biases:

Data collection by on duty MD anesthesiology Resident or DM Critical Care Residents will reduce observer and performance bias.

9. Limitation of the study:

- Single centered
- Open label
- No control group

10. Safety considerations:

Regarding the safety concerns during the measurement of optic nerve sheath diameter subjects with ocular injury, glaucoma are being excluded. The acoustic energy used for diagnostic purposes has no described adverse effects. The recent bioeffects and safety report by the American Institute of Ultrasound in Medicine (AIUM) makes no specific mention of the eye. The United States Food and Drug Administration Center for Devices and Radiological Health (US FDA/CDRH) describes an output intensity limit for all eye exposure of 50 mW/cm², recommending the use of a mechanical index (MI) < 0.23, and a thermal index (TI) < 1. The definition of an experienced operator differs, but studies have defined an experienced operator as having performed more than 25 prior transorbital ultrasound examinations.

11. Plan for Supervision and Monitoring:

The research will be continuously supervised by the co-guides [name] [name] and [name] and will be conducted under the guidance of [name].

12. Expected outcome of the Research:

Optic nerve sheath diameter changes are expected to be associated with the administration of 20% Mannitol in patients with raised intracranial pressure. Such an outcome would have various benefits in terms of usefulness of the optic nerve sheath diameter monitoring.

13. Plan for Dissemination of Research:

Research results will be submitted to the Department of Anaesthesiology and Research department, IOM.

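### Three unranked primary time points with no success, order or multiplicity rule: the stated 5% and 80% hold for each comparison alone, not for the three-part primary outcome

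*Combined protocol and SAP*

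**What the plan says.** Section 7.9, headed in the plural, gives the primary outcome as "Change in the optic nerve sheath diameter (Δ ONSD) at T₂, T₃ and T₄". These are the readings 30, 60 and 120 minutes after the infusion ends, each compared with the baseline T1. None is ranked above the others.

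Section 7.13 speaks of one outcome: "Power of the study is based on the primary outcome which is the change in ONSD following infusion of 20% Mannitol". For the analysis it says "Paired t test, chi square test will be used for data analysis" and "The value of $p < 0.05$ will be considered as statistically significant".

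Section 7.6 uses a single set of planning values, "Assuming mean difference and standard deviation of differences (σ) of 0.24 and 0.49 respectively", which give an effect size of 0.49, 35 evaluable patients and 40 enrolled. It does not say which time point they describe.

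Section 6 has one hypothesis pair for the whole serial course; the statement under test is "Serial Optic nerve sheath diameter monitoring with a cut-off value of 5.0 mm can reflect changes due to IV administration of 20% Mannitol". The first specific objective in section 5 concerns the change "brought about by administration of Mannitol within the time of its peak effect".

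No section gives a success rule (any one or all three), a testing order, a global test across the times or an adjustment for multiple tests.

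**The concern.** Three tests feed one hypothesis, and nothing says how they combine. With an any-one rule, the chance of a false claim rises above 5% when two or more times have no change. With an all-three rule, the error is safe, but power depends on the effect at each time, which section 7.6 does not state. The plan therefore does not secure 5% and 80% together for the conclusion it intends to draw.

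The rule could also be chosen after the results are seen. A reader told that ONSD changed after mannitol could not then say what error rate or power lies behind that statement.

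**Working it through.** **Inputs.** From section 7.6: two-sided alpha 0.05, power 80%, mean difference 0.24, SD of differences 0.49, effect 0.24/0.49 = 0.49, n = 35 evaluable and 40 enrolled. From sections 7.9 and 7.13: three paired t tests, each at 0.05. The correlation between the three changes is not in the documents and is an assumption.

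**1. The plan's own figure.** N = (1.96 + 0.84)² / 0.49² + 1.96² / 2 = 32.65 + 1.92 = 34.57, which rounds up to 35. For dropout, 35 / 0.9 = 38.9, so 39; the stated 40 is close. Exact noncentral-t power at n = 35 and effect 0.49 is 80.4%. The sample size is correct for one comparison.

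**2. Range of correlation.** All three changes subtract the same T1. If the readings have equal variance s² and equal correlation r, two changes have covariance s²(1 − r) and each has variance 2s²(1 − r), so they correlate at 0.5. Differences between patients in response would raise this. Zero is an extreme, for which the any-one error is 1 − 0.95³ = 14.3%.

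**3. Simulation.** Three equicorrelated two-sided paired t tests, n = 35, 200,000 replicates per setting:

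| Quantity | 0.5 | 0.7 | 0.8 | 0.9 |
|---|---|---|---|---|
| No change at any time: error, any-one rule | 12.6% | 11.1% | 9.8% | 8.5% |
| No change at any time: error, all-three rule | 0.3% | 0.8% | 1.3% | 2.2% |
| No change at any time: error, Holm | 4.5% | 4.0% | 3.5% | 3.0% |
| Effect 0.49 at one time only: false claim at another time, unadjusted | 9.2% | 8.4% | 7.8% | 7.1% |
| Same, Holm | 4.1% | 3.6% | 3.4% | 3.1% |
| Effect 0.49 at all times: power, all-three rule | 61.4% | 66.3% | 68.7% | 72.4% |
| Same: Holm power per time point | 73.3% | 72.8% | 71.9% | 71.0% |
| Same: Holm power for at least one time | 87.1% | 82.5% | 79.2% | 75.1% |

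With real change at two times, the unadjusted chance of a false claim at the third is 5.0-5.1%, so there is no inflation. At zero correlation, all-three power is 52%.

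**4. Sensitivity to the effect sizes.** The prostatectomy study in the literature review reports a greatest fall of 4.81 − 4.46 = 0.35 mm. With the SD of 0.49 from section 7.6, that is an effect of 0.71. If 0.49 is the smallest effect and the other two are 0.71 (an assumption), all-three power is 79-81% at correlation 0.5-0.9. Holm power at the 0.49 time point is then about 80%.

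**5. Peak-effect window.** The pharmacokinetics list in section 3 gives "Time of peak action: 30- 100 minutes". Counted from the end of the 20-minute infusion, the readings fall at 30, 60 and 120 minutes. Counted from its start, they fall at 50, 80 and 140. On either clock T2 and T3 lie within 30-100 minutes and T4 lies outside.

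**The case against.** The strongest reply is that the plan can be read time by time. Section 4 wants the pattern as well as the extent of change, and section 5 names the three times. In a small, uncontrolled observational thesis, reporting each comparison at 5% is a recognised convention. The hypothesis pair in section 6, whose null says that ONSD can reflect change, is weak evidence of the intended inference. This is fair. If that reading is intended, however, the plan should say so, because section 7.13 speaks of one primary outcome.

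Inflation also needs no change at two or more times, and the documents suggest otherwise. They give mannitol a duration of action of 3-6 hours, and the prostatectomy study found falls at all three of its post-dose times. This limits the likely harm but does not supply a rule.

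The power figures depend on assumptions. The 80.4% holds only where the effect is 0.49. The 0.35 mm was the greatest fall, so giving it to two times is generous; with effects 0.49, 0.49 and 0.71, all-three power is 69-76%. The SDs of that study (0.3 and 0.2) could also imply a larger effect. With uncorrelated readings, the SD of the difference is √(0.09 + 0.04) = 0.36 and the effect is 0.35/0.36 = 0.97, so adjustment would cost almost nothing at that time. The any-one rule has its own gain: power of about 95% at correlation 0.5 and 88% at 0.9, bought with uncontrolled error.

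Finally, T1 is both the eligibility reading and the baseline. Selection on T1 can shift all three changes together, and no multiplicity method corrects that. It is a separate issue, and it makes the zero-change null an idealisation.

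**Conclusion.** The concern holds. The sample size is arithmetically sound for one paired comparison, but the plan gives no rule for the three it calls primary.

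- **Any-one rule:** the error is 8.5-12.6% with no change at any time and 7.1-9.2% with real change at one time only. It returns to 5% once at most one time has no change.
- **All-three rule:** the error stays at or below 5%. Power is 61-72% if the effect is 0.49 at each time, and close to 80% only if the other two effects are clearly larger.

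These ranges assume n = 35 and equal correlations of 0.5 to 0.9, which the documents do not give. That the rule is missing does not depend on those assumptions. The point should be corrected, but it does not invalidate the design.

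**What to change.** Put this, or its equivalent, in sections 7.9 and 7.13:

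*The three paired t tests (T2, T3 and T4 versus T1) are tested with the Holm procedure at an overall two-sided 0.05. Change is claimed only at the time points that pass. All three mean changes are reported with 95% confidence intervals.*

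Say also which pattern of results answers section 6. Under Holm, requiring at least one time to pass keeps the overall error within 5%.

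A fixed testing order or one named primary time point is equally acceptable if set before data are seen. The peak-effect objective points to T2 or T3. The prostatectomy study saw its greatest fall at 90 minutes (its own T4), between this plan's T3 and T4. The choice is the investigators', with a reason given.

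In section 7.6, state that 80% is the power of a single comparison at unadjusted 0.05, say which time point 0.24 and 0.49 describe, and give the power under the chosen rule.

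**Cost.** Wording only, with no extra patients or readings.

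- **Holm:** with effects of 0.49 at all three times, power per time point falls from 80% to about 71-73% at n = 35. If all 40 complete, it is 79-80% at correlation 0.5-0.8.
- **Fixed order:** later times become descriptive once an earlier one fails.
- **Larger sample (not proposed):** holding 80% at each time at the strictest threshold, 0.05/3 = 0.0167, where n = 35 gives 64.9%, would need 47 evaluable patients. That is 47/0.9 = 52.2, so 53 enrolled.

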7.10 Expected Duration of the Study: 6 months

7.11 Tools and techniques for data collection:

Tools:

- 6-10 Hz linear array USG probe (Sonosite M-Turbo)
- Ultrasound coupling jelly
- Transparent dressing (Tegaderm)
- Cleaning gauze pieces
- Proforma
- Arterial blood pressure monitor (invasive or non-invasive)

Methodology:

- Included patients will be those above 18 years, admitted in the ICU of TUTH, Maharajgunj, with the diagnosis of traumatic brain injury, acute stroke or intracranial hemorrhage and under osmotherapy with 20% Mannitol.
- Written informed consent will be taken from the patient or patient's responsible guardian. Conscious patients will be explained about the procedure.
- The patient's diagnosis, epidemiological variables and baseline variables will be recorded.
- Baseline ventilator parameters will be noted and the ICU staffs instructed not to change those variables over the study period until deemed necessary by the treating physician.
- Positioning of the patient will be done: supine, 30° head elevated.
- Mean arterial blood pressure will be noted from arterial line readings or NIBP reading as appropriate or available.
- A protective transparent dressing will be placed over the closed eyelid in sedated or ventilated patients as an additional measure to prevent any irritation of the conjunctiva.
- For ONSD measurement, generous amount of coupling gel will be applied over the closed upper eyelid.
- The probe will be held with a pincer grasp between the thumb and index finger, using the remaining fingers for stability by resting them on the maxilla or supraorbital ridge.
- The depth will be adjusted to optimize the visualization of the intended structures, i.e. the optic nerve, the surrounding CSF space and the ONS. The gain will be adjusted to create a hypoechoic posterior chamber.
- The mechanical index will be adjusted as per the recommended values for the eye, in order to limit the amount of energy absorbed by the eye.
- Values will be noted 0.3 cm posterior to the retinal surface after optimal visualization of the entry of optic nerve in the orbit.

- Mean will be obtained after taking 3 readings in each eye. Only patients with mean ONSD > 0.5cm will be included and the baseline value designated as T₁.
- Intravenous 20% Mannitol as prescribed will be administered via a dedicated IV line over 20 minutes.
- Mean arterial pressure and Optic nerve sheath diameter readings will be performed as previously described and noted at 30(T₂), 60(T₃) and 120(T₄) minutes after completion of IV administration.
- The coupling gel will be removed gently after each measurement and the protective adhesive dressing will be removed at the end of the study.

[figure not shown]
7.12 Management protocol of patients/participants if applicable:

All patients will be managed according to the current ICU protocol abiding with the ENLS and Brain Trauma Foundation guidelines for TBI and intra-cerebral hemorrhage and AHA/ASA guidelines for acute ischemic stroke. In subjects with persistently elevated intracranial pressure and ONSD findings above 5.0 mm despite the administration of 20% Mannitol, decision for further treatment will rest upon the treating physician.

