Raised intracranial pressure is a common incidence and complication in critically ill patients. There have been intense studies and research for understanding the underlying patho-physiology and treatment. Much of our understanding of the intracranial pressure is based on the Monro-Kellie hypothesis which states that the sum of intracranial volumes of blood, brain, CSF and other components is constant, and that an increase in any one of these must be offset by an equal decrease in another or else the pressure increases.¹ The normal ICP is defined as 5 to 15 mmHg (7.5-20 cmH₂O). Under normal conditions the brain is able to auto-regulate its blood flow. Cerebral perfusion pressure (CPP) defined by the equation $CPP = MAP - ICP$, is the single-most important determinant of this auto-regulation. Within a CPP ranging from 50-150 mmHg, the auto-regulation is intact. However during any insult/injury this ability of the brain may be impaired or absent thus leading to an unregulated change in ICP. Trauma, intracranial hemorrhage, intracranial tumors and ischemic stroke are the major causes of such insult and raised intracranial pressure.² Prompt diagnosis and treatment of elevated intracranial pressure is the cornerstone of management in TBI, intracranial hemorrhages and acute stroke and has been associated with poor outcomes. Care based on ICP monitoring has been proved to be associated with frequency of good recovery and favorable outcome.³ Such monitoring can be invasive or non-invasive. Currently, invasive ICP monitoring is the gold standard. External ventricular drainage and micro-transducer ICP monitoring devices are the commonly used modes for ICP monitoring. However there are various hazards (infection and hemorrhage) of such invasive procedures and few studies have shown no such difference in outcomes with or without invasive monitoring.^{4, 5}

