There have been various validated modes of non-invasive ICP monitoring. Trans-cranial Doppler ultrasonography (TCD), optic nerve sheath diameter (ONSD), tympanic membrane displacement and fundoscopic examinations have been proposed as being surrogates to invasive ICP monitoring.^{3,4} There have been many studies comparing the use of invasive against the use of non-invasive modes of ICP monitoring. Among these Optic nerve sheath diameter (ONSD) can be taken as the simplest mode with high positive and negative predictive values on detecting rise in intracranial pressure.⁶ It's correlation with invasively measured intracranial pressure and imaging findings has also been validated⁷ and used extensively in diagnosing episodes of raised intracranial pressure in emergency departments, intensive and neurosurgical units.⁸

The optic nerve is part of the central nervous system and therefore surrounded by the dural sheath. Between the sheath and the white matter is a small 0.1-0.2 mm subarachnoid space which communicates with the intracranial subarachnoid space. In cases with raised intracranial pressure the pressure is also transmitted into this sheath and expansion occurs. This expansion is appreciable via various imaging modalities like CT scans, MRI and ultrasonographic imaging. The feasibility and simplicity of this measurement by ultrasonography has made it a efficient tool in diagnosing and monitoring in acute care setup. The major drawbacks are the inter-observer variation in measurement and conditions that may confound the finding such as tumors, inflammation, grave's disease and sarcoidosis. Change in ONSD measurements performed before and after interventions including hyperventilation, drainage of CSF, administration of Mannitol, tracheal manipulation and lumbar puncture appear to correlate well with the induced change in ICP.^{6,7}

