Launey et. al,¹⁵ performed a study to determine the rate of ONSD variation after Mannitol administration for increased ICP episodes. They included thirteen patients in their study comparing and correlating the changes in ONSD, pulsatility index and invasively monitored ICP. The ONSD significantly decreased after Mannitol infusion from 6.3 to 5.56mm (p=0.0007). Concomitantly the intracranial pressure also decreased for 35(32-41) to 25(22-29)mmHg (p=0.001) and the CPP increased from 47 to 69 (p=0.003). The study concluded that the variations of ONSD appear to be an interesting and effective parameter to evaluate the efficacy of osmotherapy for elevated ICP episodes in patients with acute brain injury/SAH.

A study by Li-juan Wang et al¹⁶ which included 60 patients who underwent measurement of ONSD prior to lumbar puncture on admission and during follow up, concluded that ICP was strongly correlated with ONSD(r=0.758, p<0.001) and this association was independent of all other factors like age, sex, BMI, mean arterial pressure and diastolic blood pressure. It also states that ultrasonographic ONSD measurements provide a potential noninvasive method to quantify ICP that can be conducted at the bedside.

Another study performed in the Indian population by Shirodkar et. al¹⁷ evaluated the efficacy of ONSD by ultrasonography as a non-invasive method for detecting raised intracranial pressure in intensive care unit to compare with CT/MRI findings of raised ICP and to prognosticate ONSD value with treatment. The results showed a sensitivity of detecting raised ICP by ONSD to be 84.6% and a specificity approaching around 99%.

A study by Joushua E Nash et al¹⁸ uses ONSD to diagnose raised ICP along with correlation with CT findings. It also reviews the literature from the past and concludes that <0.50 cm ONSD ensured normal pressure (95% CI 0.469-0.540, p<0.001). The study also quantifies the inter-observer variability in ONSD measurement (0.001-0.002cm). The study also determines the expertise required for measuring ONSD to be around 10-25 case examinations and this has been supported by various other studies.

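### Further ICP-lowering treatment after mannitol is permitted but neither recorded nor handled, so the ONSD change at T3 and T4 may be overstated

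*Combined protocol and SAP*

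**What the plan says.** The primary outcome (7.9) is "Change in the optic nerve sheath diameter (Δ ONSD) at T₂, T₃ and T₄". The methodology (7.11) has readings "noted at 30(T₂), 60(T₃) and 120(T₄) minutes after completion of IV administration", following a 20-minute infusion. The first specific objective (section 5) attributes the changes to mannitol, and section 9 lists the absence of a control group as a limitation.

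Section 7.12 puts all patients under the current ICU protocol and guidelines. For those with persistently raised ICP and "ONSD findings above 5.0 mm despite the administration of 20% Mannitol, decision for further treatment will rest upon the treating physician". It says nothing about when such treatment may start.

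The variables in 7.8 and the proforma in section 19 cover mannitol dose, blood pressure, ONSD, GCS and baseline ventilator pressures, and the proforma adds mannitol and reading times. Neither has a field for further treatment. Section 7.11 asks staff to hold ventilator settings unless the physician judges a change necessary, but PIP and PEEP are recorded only at baseline. Section 7.13 names a paired t test and a chi-square test, with no rule for readings taken after further treatment.

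**The concern.** The introduction itself says that ONSD responds to more than mannitol: changes around "interventions including hyperventilation, drainage of CSF, administration of Mannitol, tracheal manipulation and lumbar puncture appear to correlate well with the induced change in ICP". A second ICP-lowering measure given between readings would therefore be expected to move the primary endpoint. In an uncontrolled before/after comparison that movement cannot be separated from mannitol's own effect unless it is recorded.

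The trigger may not be rare. Entry requires ONSD above 5 mm, the same cut-off that 7.12 uses. In the cited study of mannitol for raised ICP, "The ONSD significantly decreased after Mannitol infusion from 6.3 to 5.56mm" and "the intracranial pressure also decreased for 35(32-41) to 25(22-29)mmHg". Both final averages are above the protocol's own limits, since "The normal ICP is defined as 5 to 15 mmHg". The rationale (section 4) adds "In absence of invasive monitoring in a limited setup like ours", so ICP is not measured directly here and the study's ONSD reading is a natural prompt for escalation.

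At stake is the size of the change at T3 and T4, two of the three primary time points. Whether ONSD falls soon after mannitol is much less affected.

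**Working it through.** **1. The plan's own figure (7.6).** Inputs: two-sided alpha 0.05, power 80%, mean difference 0.24, SD of differences 0.49, effect size 0.49.

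N = (1.96 + 0.84)² / 0.49² + 1.96² / 2 = 32.65 + 1.92 = 34.57, so 35. This reproduces the plan, and nothing here disputes it.

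**2. Timing (7.11).** A T2 reading above 5.0 mm is known 60 − 30 = 30 minutes before T3 and 120 − 30 = 90 minutes before T4. T4 is 20 + 120 = 140 minutes from the start of the infusion.

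**3. How often the ONSD condition might be met.** A patient whose fall equals the planned 0.24 mm stays above 5.0 mm if baseline exceeds 5.24 mm. Assuming a normal baseline with mean 5.5 to 6.3 mm and SD 0.4 to 0.7 mm, cut at 5.0 mm, and a change with mean fall 0.24 and SD 0.49, the share still above 5.0 mm at T2 is 71% to 95%. This covers only the ONSD half of the trigger. It is not the share treated, which the documents do not give.

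**4. Size of the overstatement.** If a share f is treated before a reading and falls a further g mm by then, the mean fall is overstated by f × g. All values of f and g below are assumed.

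| Treated of 35 | Extra fall (mm) | Overstatement (mm) | Relative to 0.24 mm |
|---|---|---|---|
| 1 | 0.5 | 0.014 | 6% |
| 4 | 0.3 | 0.034 | 14% |
| 7 | 0.3 | 0.060 | 25% |
| 7 | 0.5 | 0.100 | 42% |

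A true 0.24 mm fall would thus read 0.27, 0.30 or 0.34 mm in the last three rows.

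**5. The extreme case for the test.** Suppose nothing of mannitol's effect remained at T4, f = 20% and g = 0.5 mm. The mean shift is 0.10 mm and the SD is √(0.49² + 0.2 × 0.8 × 0.5²) = 0.53. The paired t test with n = 35 (noncentral t) then rejects with probability about 0.19 instead of 0.05.

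**6. Behaviour of carry-forward.** Replacing readings after further treatment with the last one before it, with 7 of 35 (20%) treated at random after T2 and a true T2 fall of 0.24 mm, gives 0.8 × (T4 fall) + 0.2 × 0.24:
- true T4 fall 0.24: 0.24 mm, unbiased;
- true T4 fall 0.12: 0.096 + 0.048 = 0.144 mm, too large;
- true T4 fall 0: 0.048 mm, too large.

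If the effect is sustained at 0.24 mm but treatment is selective, simulation (bivariate normal changes, SD 0.49, T2–T4 correlation 0.3 to 0.8) gives 0.17 to 0.22 mm when the highest T2 levels are treated and 0.15 to 0.21 mm when the worst responders are: too small.

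**The case against.** The strongest reply is that exposure before T4 is inferred. Section 7.12 is a general care clause that requires both persistently raised ICP and a high ONSD. The introduction puts mannitol's peak action at 30 to 100 minutes, so escalating straight after the 30-minute reading would be early, and the flow figure, which might settle timing, is not shown. This stands as far as it goes: treatment before T4 is possible, not shown to be planned or common.

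A reader might also infer that the plan is likely to produce a false claim of lasting effect at T4. The documents do not support that. They give mannitol a duration of 3 to 6 hours, and T4 is about 140 minutes from the start of infusion. In the cited prostatectomy study the greatest fall was at 90 minutes after mannitol, the last of its three post-mannitol readings in the Trendelenburg position. The 19% rejection rate in step 5 needs the effect to have gone by T4, which these facts make less likely.

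Partial safeguards exist: ventilator settings are held unless the physician intervenes, position is fixed, and decompressive surgery is an exclusion. None covers repeat osmotherapy, sedation or CSF drainage. The proforma's inpatient number and reading times would allow the hospital record to be consulted, so the gap is not beyond repair. The protocol does not plan this, however, and 7.13 has the study data destroyed after completion.

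**Conclusion.** The point holds as a risk of overstated size at T3 and T4. It is more than missing detail: followed as written, the plan can credit later care to mannitol with no planned way to see it. The amount is unknown. The 0.03 to 0.10 mm illustration rests wholly on an assumed 4 to 7 of 35 treated and an assumed 0.3 to 0.5 mm extra fall. If few or none are treated early, the effect is negligible. T2 is least exposed but not immune, since care could also be escalated within 30 minutes of the infusion ending. The documents do not support reading this as invalidating the study or its early result. It is a cheap improvement.

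**What to change.** **Proforma and 7.8.** Add the type and clock time of any further ICP-lowering treatment and any ventilator change from T1 to T4. Record PIP and PEEP at each reading in ventilated patients.

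**Section 7.13.** Report the number treated before each time point. Keep the all-patient paired analysis as the main one. Add one sensitivity analysis that carries forward the last reading before further treatment. State that it can err either way: too small a fall if poor responders are the ones treated, too large if the effect is waning. It should not be labelled conservative.

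**Wording of results.** If more than a trivial number are treated before T3 or T4, or the sensitivity result differs materially, describe those results as change after mannitol plus later care. A single treated patient, worth about 0.014 mm even at 0.5 mm extra, should not trigger this.

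**Cost.** A few proforma lines, one extra analysis and possibly a more cautious T3/T4 conclusion. Sample size and clinical care are unchanged; treatment should not be withheld to protect the readings.
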